Record subject satisfaction with pain management						Λ	Λ	Λ	Λ	Λ
time ICF is signed)	▲									

Table 1: Time and Events Schedule of Study Procedures (Day 1 - Day 180)

Abbreviations: AE = adverse event; d = day; h = hours; ICF = informed consent form; min = minutes; NRS = numeric rating scale; PGIC = Patient Global Impression of Change; RFA = radiofrequency ablation; SSDI = Social Security disability insurance

1 Vital signs will be measured after the subject has rested in a seated position for at least 5 minutes.

2 Administer pain intensity NRS prior to iovera/RFA.

Table 2: Time and Events Schedule of Study Procedures (Day 210 - 360)

	Day 210 Call	Day 240 Call	Day 270 Call	Day 300 Call	Day 330 Call	Day 30 Visit	Day 360 Call
Time Window	±7d						
Record NRS pain intensity scores (pain "right now")	Х	Х	Х	Х	Х	Х	Х
Record NRS pain intensity scores (worst / average pain over 24h)	Х	Х	Х	Х	Х	Х	Х
Administer the Oswestry Disability Index	Х	Х	Х	Х	Х	Х	Х
Administer the PGIC	Х	Х	Х	Х	Х	Х	Х
Record concomitant medications (including opioids and analgesics)	Х	Х	Х	Х	Х	Х	Х
Record subject satisfaction with pain management	Х	Х	Х	Х	Х	Х	Х
Record AEs and adverse device effects (beginning at the time ICF is signed)	•						

Abbreviations: AE = adverse event; d = day; h = hours; NRS = numeric rating scale; PGIC = Patient Global Impression of Change

LIST OF ACRONYMS/ABBREVIATIONS

AE	Adverse event
CLBP	Chronic low back pain
cm	Centimeter
COVID-19	Coronavirus disease 2019
CRF	Case report form
d	Day
DO	Doctor of Osteopathic Medicine
EDC	Electronic data capture
h	Hours
Hz	Hertz
ICF	Informed consent form
IV	Intravenous
L	Lumbar
MBB	Medial branch block
MDR	Medical device report
MED	Morphine equivalent dose
mL	Milliliter
MRI	Magnetic resonance imaging
N ₂ O	Nitrous oxide
NRS	Numeric rating scale
NSAIDs	Non-steroidal anti-inflammatory drugs
ODI	Oswestry Disability Index
PGIC	Patient Global Impression of Change
RCT	Randomized controlled trial
RF	Radiofrequency
RFA	Radiofrequency ablation
S	Sacral
SAE	Serious adverse event
SD	Standard deviation
SOC	Standard of care
SSDI	Social Security disability insurance
TEAEs	Treatment-emergent adverse events
US	United States

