Given the COVID-19 pandemic, the subject must be medically fit/cleared for treatment by the investigator. If there is a concern about a subject's recent or potential exposure to COVID-19, or if the subject is not medically fit/cleared for treatment due to suspected COVID-19 illness/symptoms (or other serious illness), the subject must be excluded per *Exclusion criterion #4*.

Study Device:

Name: iovera° System

Duration of Subject Participation in Study:

Participation will begin at the signing of the study ICF. No more than 30 days should pass between signing of the ICF and the iovera^o or RFA treatment procedure. Subjects will be followed up for 360 days (\pm 7 days) after iovera^o or RFA treatment. Therefore, subjects may participate in the study for up to 392 days.

Study Stopping Rules

The study may be terminated if the Investigator, or officials from regulatory authorities identify conditions during the study that indicate so.

The Investigator will review all serious adverse device effects and serious adverse events (SAEs) reported from the clinical study on an ongoing basis and in real time (i.e., as the events are reported). The Investigator will be responsible for temporarily halting the study if the type, frequency, or seriousness/severity of such events suggests a potential threat to the safety of the study participants. If such action is taken, a thorough review of all available data will be conducted. Based on the results of this review and discussions with the Investigator and/or regulatory authorities as warranted, the study may be restarted or permanently terminated.

In addition, any death will be thore	oughly reviewed, and a	appropriate action taken.	

Removal of Subjects from Therapy or Assessment

Every reasonable effort will be made to maintain subject compliance and participation in the study. Reasons for discontinuation of any subject from the study will be recorded.

If any clinically significant event or condition is uncovered during the study period that might render the subject medically unstable or compromise the subject's post-treatment course, the subject will be withdrawn from the study and the event or condition will be reported as an AE or SAE.

If a subject withdraws from the study and has an ongoing AE, every effort will be made to follow up on such events until satisfactory resolution is obtained or further follow-up is otherwise no longer warranted.

Withdrawal Secondary to Adverse Events

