If a subject, experiences an AE that renders the subject incapable of continuing with the remaining assessments, the subject will be discontinued from further participation in the study. A final evaluation, including the early termination assessments will be performed so that the subject's study participation can be terminated in a safe and orderly manner.

Any subject who discontinues because of an AE will be instructed to notify the study personnel of any abnormal symptoms and to visit the study site if medical evaluation is needed and the urgency of the situation permits. Any subject exhibiting AEs will receive appropriate treatment at the discretion of the Investigator until resolution of the AE.

This study involves a single treatment (i.e., iovera° or RFA); therefore, subjects will not be terminated from the ongoing study assessments as long as they are willing and able to continue with the follow-up schedule according to the protocol. For emergencies and other unscheduled visits to a medical facility other than the study site, medical records will be obtained by the Investigator and appropriate information captured in the subject's case report form (CRF). After termination from the study, the subject may be followed for safety including monitoring of AEs through Day 360.

Voluntary or Study Investigator Withdrawal

Subjects are free to discontinue from the study at any time, without prejudice to future treatment. A subject may be discontinued from the study if the subject refuses study treatment or refuses to comply with study procedures. Subjects will be encouraged to complete the study safety assessments. Reasons for discontinuation from the study will be recorded.

Early Termination Assessments

In case of early termination, the following assessments shall be performed:

- Record date, time, and reason of withdrawal
- Review adverse events; any ongoing AEs/SAEs will need to be followed to resolution

l		1
Name of Sponsor/Company:		
The Albany & Saratoga Centers		
For Pain Management		
Name of Device:		
iovera° System		
Record responses to pain assessment:		
 Pain intensity scores on the NRS as "How mu your low back right now?" 	ch pain are you ex	periencing in
 Pain intensity scores on the NRS as "What wa hours in your low back?" 	as your worst pain	in the past 24
 Pain intensity scores on the NRS as "What wa 24 hours in your low back?" 	as your average pa	in in the past
Clinical Assessments:		

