9.1.1. Handling Missing Values

9.1.1.1. NRS Pain Intensity Scores from Day of iovera^o/RFA treatment from 24hr after treatment to Day X (7, 15, 30, 60, 90, 120, 150, 180, 210, 240, 270, 300, and 360)

For subjects who drop out of the study early because of a related AE or lack of efficacy, their later missing timepoints will be imputed using worst-observation-carried-forward (WOCF) method, in which their worst observation since the first daily pain assessment will be carried to Day 15 (or subsequent days), For subjects dropping out early for any other reason, last-observation-carried-forward (LOCF) imputation will be used.

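### Two protocol passages disagree on whether a treated subject with a potentially destabilising event is withdrawn or kept in follow-up; following the first makes Day 360 data missing for outcome-linked reasons

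*Protocol*

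**What the plan says.** Protocol, Removal of Subjects from Therapy or Assessment, gives a mandatory rule for a clinically significant event or condition found during the study period. Trigger and consequence read: "that might render the subject medically unstable or compromise the subject's post-treatment course, the subject will be withdrawn from the study". In full, the consequence is that "the subject will be withdrawn from the study and the event or condition will be reported as an AE or SAE". It makes no exception for subjects already treated. The same section says of adverse events (AEs) ongoing at withdrawal that "every effort will be made to follow up on such events until satisfactory resolution is obtained" or until follow-up is no longer warranted.

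Protocol, Withdrawal Secondary to Adverse Events, has a narrower trigger. If a subject "experiences an AE that renders the subject incapable of continuing with the remaining assessments, the subject will be discontinued" from further participation. It then points out that treatment is a single procedure and concludes that "subjects will not be terminated from the ongoing study assessments as long as they are willing and able to continue with the follow-up schedule". On safety after leaving, it says: "After termination from the study, the subject may be followed for safety including monitoring of AEs through Day 360".

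Protocol, Early Termination Assessments, requires the withdrawal reason, an AE review with ongoing events followed to resolution, and the three Numeric Rating Scale (NRS) pain items. As published, the list does not include the Oswestry Disability Index (ODI), Patient Global Impression of Change (PGIC) or satisfaction.

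Protocol, Collection and Assessment of Adverse Device Events and Adverse Drug Events, has all adverse events collected from consent to Day 360, with no exception for withdrawn subjects.

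SAP 9.7.2.1.1 sets the primary efficacy comparison on average-pain NRS at Day 360. SAP 9.1.1.1 fills missing NRS by worst observation carried forward (WOCF) when dropout is due to a related AE or lack of efficacy. Otherwise: "For subjects dropping out early for any other reason, last-observation-carried-forward (LOCF) imputation will be used". The SAP gives no imputation rule for ODI, PGIC or satisfaction.

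**The concern.** The protocol does not settle whether a subject who has had the procedure, has a worrying event and is still content to take the study calls should remain under observation. If the site applies the withdrawal rule, scheduled outcome collection stops because of the subject's clinical course. That is informative missingness, and it falls on the subjects whose results matter most in a study with safety in its primary objective.

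An observed Day 360 pain score is then replaced by an imputed one, and the imputation depends on the reason recorded for dropout. For ODI, PGIC and satisfaction there is simply no value. For safety, one section makes AE monitoring after termination discretionary, while another collects all AEs to Day 360. Two subjects with the same course could therefore contribute different data, depending on which sentence the site follows.

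**Working it through.** There is no plan figure to reproduce: SAP 10 fixes 15 per arm without a power basis and states no dropout rate. The check is mainly a comparison of texts.

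**1. Where the two withdrawal texts conflict**

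| Subject | Removal of Subjects section | Withdrawal Secondary to AEs section | Result |
|---|---|---|---|
| Not yet treated, trigger met | withdrawn | retention statement hardly applies | no practical conflict |
| Treated, AE leaves subject unable to do assessments | withdrawn if trigger met | discontinued | agree |
| Treated, trigger met, unwilling to continue | withdrawn | no duty to retain | agree |
| Treated, trigger met, willing and able | withdrawn | not terminated from assessments | **contradiction** |

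**2. What stops if the withdrawal rule is followed**

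ODI, PGIC and satisfaction are scheduled every 30 days from Day 30 to Day 360, that is 360/30 = 12 post-treatment time points. A subject withdrawn just after Day 30 would lose 11 of the 12 (Days 60 to 360). NRS is lost at the same 11 times, apart from the early-termination score.

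**3. What replaces the Day 360 NRS**

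WOCF takes the worst post-treatment score, and last observation carried forward (LOCF) takes the last. For the same subject WOCF is therefore never lower than LOCF. With an assumed worst score of 8 and last score of 4, changing the recorded reason moves the unadjusted arm mean by (8 − 4)/15 = 0.27 points.

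Neither value need match the true Day 360 score. If the imputed value is wrong by g points in w subjects of a 15-subject arm, the unadjusted arm mean is wrong by w × g / 15, in either direction. Both w and g are assumptions:

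| w (share of arm, w/15) | g = 2 | g = 4 | g = 6 |
|---|---|---|---|
| 1 (6.7%) | 0.13 | 0.27 | 0.40 |
| 2 (13.3%) | 0.27 | 0.53 | 0.80 |
| 3 (20.0%) | 0.40 | 0.80 | 1.20 |

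On a 0 to 10 scale the limit per subject is 10/15 = 0.67 points.

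**4. Safety counts**

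SAP 8 puts every treated subject in the safety set, and SAP 9.1 uses the analysis-set count as the denominator. The denominator therefore stays at 15. If a withdrawn subject's only event in a category occurs after termination and is not captured, the reported incidence is too low by 1/15 = 6.7 percentage points.

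**The case against.** The strongest reply is that the two sections can be read together. The second is the specific rule for AEs in treated subjects, and being able to continue can be taken to include being medically stable. That narrows the conflict, but does not remove it. The first rule is triggered by what *might* happen, and a subject at risk of instability can still be able to answer a telephone call.

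The documents also do not support several stronger readings that a reader might infer:

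- *Any clinically significant event forces withdrawal.* The trigger is limited to events that might cause instability or compromise the post-treatment course, although that wording is broad.
- *Withdrawal does nothing except end data collection.* The rule can also apply between consent and the procedure, up to 30 days. After treatment, the protocol's Clinical Assessments section bars lumbar and sacral injections, so leaving the study may have a clinical purpose.
- *Safety data are lost.* The triggering event is reported, ongoing AEs are followed to resolution, and AE collection to Day 360 is stated elsewhere. The gap is confined to new AEs after termination.
- *LOCF flatters the arm by carrying an early, favourable score.* The documents give no time course of relief. An NRS is required at early termination, and the SAP does not exclude it, so the carried score may well postdate the event. The bias could go either way.
- *The safety denominator shrinks.* With zero events seen, taking n from 15 to 12 would raise the one-sided 95% upper bound from 1 − 0.05^(1/15) = 18.1% to 1 − 0.05^(1/12) = 22.1%. SAP 8 and 9.1 keep all treated subjects in the denominator, so this calculation does not describe the planned analysis.

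It is also fair to say that choosing WOCF or LOCF by dropout reason applies to every dropout, and is not created by the withdrawal rule. The rule adds avoidable cases to it.

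**Conclusion.** The contradiction is real and confined to treated subjects who meet the withdrawal trigger and remain willing and able to continue. For them, following the withdrawal rule turns observable Day 360 outcomes into missing ones for reasons linked to outcome. It also leaves capture of new AEs discretionary, at odds with the protocol's own collection period.

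Each such subject is 6.7% of an arm. The arm-mean error of 0.13 to 1.20 NRS points rests on assumed withdrawals of one to three and assumed imputation errors of 2 to 6 points. The documents fix neither the number affected nor the direction of bias. Loss is a risk that depends on which text the site follows; it is not a certain result. Which withdrawal trigger is clinically right is not judged here.

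**What to change.** 1. Reconcile Removal of Subjects from Therapy or Assessment with Withdrawal Secondary to Adverse Events. The clinical trigger is for the sponsor and investigator to settle.
2. Separate withdrawal from data collection. State that treated subjects who consent and are able continue the scheduled AE, NRS, ODI, PGIC and satisfaction assessments through Day 360, whatever the withdrawal decision.
3. Make safety follow-up after termination definite, subject to consent, instead of optional, in line with the AE collection period already stated.

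SAP 9.1.1.1 imputes missing time points, so scores observed after withdrawal would simply be used. The cost is protocol wording and some continued calls and visits that are already in Tables 1 and 2.

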Appendix 1: Subject's Reported Pain (Numeric Rating Scale)

Subjects will evaluate their pain in the low back region using an 11-point Numeric Rating Scale (NRS), where 0=no pain and 10=worst possible pain.

The timepoints and assessments are as follows:

Current Pain (Pain "right now")	Daily Pain (Worst/Average pain over 24 hours)
At screening	At screening
Day of iovera° or RFA treatment (pretreatment), once daily Days 1-6 (at 6 pm ±4 hours) after treatment, at Day 7 (± 2 days), Day 15 (± 2 days), Day 30 (± 5 days), Day 60 (± 5 days), Day 90 (± 5 days), Day 120 (± 5 days), Day 150 (± 5 days), Day 180 (± 5 days), Day 210 (± 7 days), Day 240 (± 7 days), Day 270 (± 7 days), Day 300 (± 7 days), Day 330 (± 7 days), Day 360 (± 7 days)	Once daily Days 1-6 (at 6 pm ±4 hours) after treatment, at Day 7 (± 2 days), Day 15 (± 2 days), Day 30 (± 5 days), Day 60 (± 5 days), Day 90 (± 5 days), Day 120 (± 5 days), Day 150 (± 5 days), Day 180 (± 5 days), Day 210 (± 7 days), Day 240 (± 7 days), Day 270 (± 7 days), Day 300 (± 7 days), Day 330 (± 7 days), Day 360 (± 7 days)

**Current Pain:** Subjects will evaluate how much pain they are currently experiencing (i.e., "How much pain are you experiencing in your low back **right now**?") at Screening, day of iovera^o treatment (pretreatment), once daily (at 6 pm ±4 hours) from prior to iovera^o treatment to Days 1-6, at Day 7 (\pm 2 days), Day 15 (\pm 2 days), Day 30 (\pm 5 days), Day 60 (\pm 5 days), Day 90 (\pm 5 days), Day 120 (\pm 5 days), Day 150 (\pm 5 days), Day 180 (\pm 5 days), Day 210 (\pm 7 days), Day 240 (\pm 7 days), Day 270 (\pm 7 days), Day 300 (\pm 7 days), Day 330 (\pm 7 days), Day 360 (\pm 7 days):

Pain Intensity Scale (Current Pain)

On a scale of 0 to 10, where 0 = no pain and 10 = worst possible pain, circle the number that best describes your answer to the question "How much pain are you experiencing in your low back **right now**?" (Circle one number only.)

0 1 2 3 4 5 6 7 8 9 10

No pain

Worst possible pain

Daily Pain: Subjects will evaluate their *worst* and *average* level of pain over the past 24 hours at Screening, once daily (at 6 pm ±4 hours) from prior to iovera° treatment to Day Days 1-6, at Day 7 (\pm 2 days), Day 15 (\pm 2 days), Day 30 (\pm 5 days), Day 60 (\pm 5 days), Day 90 (\pm 5 days), Day 120 (\pm 5 days), Day 150 (\pm 5 days), Day 180 (\pm 5 days), Day 210 (\pm 7 days), Day 240 (\pm 7 days), Day 270 (\pm 7 days), Day 300 (\pm 7 days), Day 330 (\pm 7 days), Day 360 (\pm 7 days):

```
CONFIDENTIAL
```

Pain Intensity Scale (Daily Pain)

On a scale of 0 to 10, where 0 = no pain and 10 = worst possible pain, circle the number that best describes your answer to the question "What was your **worst** pain in the past 24 hours in your low back?" (Circle one number only.)

0 1 2 3 4 5 6 7 8 9 10

No pain

Worst possible pain

On a scale of 0 to 10, where 0 = no pain and 10 = worst possible pain, circle the number that best describes your answer to the question "What was your **average** pain in the last 24 hours in your low back?" (Circle one number only.)

0 1 2 3 4 5 6 7 8 9 10

No pain

Worst possible pain

Appendix 2: Subject Satisfaction Assessments (Likert Scale)

Subject satisfaction with pain management will be assessed using Likert scales.

Subject Satisfaction with Pain Management

The subject's satisfaction with pain management will be conducted at Day 30 (\pm 5 days), Day 60 (\pm 5 days), Day 90 (\pm 5 days), Day 120 (\pm 5 days), Day 150 (\pm 5 days), Day 180 (\pm 5 days), Day 210 (\pm 7 days), Day 240 (\pm 7 days), Day 270 (\pm 7 days), Day 300 (\pm 7 days), Day 330 (\pm 7 days), Day 360 (\pm 7 days).

Subject Satisfaction with Pain Management

Please circle the number below that best describes your overall satisfaction with your pain management. (Select one number only)

- 1. Extremely dissatisfied
- 2. Dissatisfied
- 3. Neither satisfied nor dissatisfied
- 4. Satisfied
- 5. Extremely satisfied

Appendix 3: Oswestry Disability Index (ODI)

Subjects will complete the ODI at Screening, Day 30 (\pm 5 days), Day 60 (\pm 5 days), Day 90 (\pm 5 days), Day 120 (\pm 5 days), Day 150 (\pm 5 days), Day 180 (\pm 5 days), Day 210 (\pm 7 days), Day 240 (\pm 7 days), Day 270 (\pm 7 days), Day 300 (\pm 7 days), Day 330 (\pm 7 days), Day 360 (\pm 7 days):

Oswestry Low Back Pain Disability Questionnaire

Instructions

This questionnaire has been designed to give us information as to how your back or leg pain is affecting your ability to manage in everyday life. Please answer by checking ONE box in each section for the statement which best applies to you. We realise you may consider that two or more statements in any one section apply but please just shade out the spot that indicates the statement which most clearly describes your problem.

Section 3 - Lifting

Section 1 - Pain intensity

I have no pain at the moment I can lift heavy weights without extra pain The pain is very mild at the moment I can lift heavy weights but it gives extra pain The pain is moderate at the moment Pain prevents me from lifting heavy weights off the floor, but I can manage if they are The pain is fairly severe at the moment conveniently placed eg. on a table The pain is very severe at the moment Pain prevents me from lifting heavy weights, but I can manage light to medium weights if The pain is the worst imaginable at the they are conveniently positioned moment I can lift very light weights Section 2 – Personal care (washing, dressing etc) I cannot lift or carry anything at all I can look after myself normally without causing extra pain Section 4 – Walking* I can look after myself normally but it Pain does not prevent me walking any distance causes extra pain Pain prevents me from walking more than It is painful to look after myself and I am 1 mile slow and careful Pain prevents me from walking more than I need some help but manage most of my 1/2 mile personal care Pain prevents me from walking more than I need help every day in most aspects of 100 yards self-care I can only walk using a stick or crutches I do not get dressed, I wash with difficulty and stay in bed I am in bed most of the time

Section 5 – Sitting

- I can sit in any chair as long as I like
- I can only sit in my favourite chair as long as I like
- Pain prevents me sitting more than one hour
- Pain prevents me from sitting more than 30 minutes
- Pain prevents me from sitting more than 10 minutes
- Pain prevents me from sitting at all

Section 6 - Standing

- I can stand as long as I want without extra pain
- I can stand as long as I want but it gives me extra pain
- Pain prevents me from standing for more than 1 hour
- Pain prevents me from standing for more than 3 minutes
- Pain prevents me from standing for more than 10 minutes
- Pain prevents me from standing at all

Section 7 - Sleeping

- My sleep is never disturbed by pain
- My sleep is occasionally disturbed by pain
- Because of pain I have less than 6 hours sleep
- Because of pain I have less than 4 hours sleep
- Because of pain I have less than 2 hours sleep
- Pain prevents me from sleeping at all

Section 8 – Sex life (if applicable)

- My sex life is normal and causes no extra pain
- My sex life is normal but causes some extra pain
- My sex life is nearly normal but is very painful
- My sex life is severely restricted by pain
- My sex life is nearly absent because of pain
- Pain prevents any sex life at all

Section 9 - Social life

- My social life is normal and gives me no extra pain
- My social life is normal but increases the degree of pain
- Pain has no significant effect on my social life apart from limiting my more energetic interests eg, sport
- Pain has restricted my social life and I do not go out as often
- Pain has restricted my social life to my home
- I have no social life because of pain

Section 10 – Travelling

- I can travel anywhere without pain
- I can travel anywhere but it gives me extra pain
- Pain is bad but I manage journeys over two hours
- Pain restricts me to journeys of less than one hour
- Pain restricts me to short necessary journeys under 30 minutes
- Pain prevents me from travelling except to receive treatment

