9.7.1.2. Secondary Endpoints

The following endpoints are secondary efficacy endpoints:

- NRS "average pain over past 24 hours" intensity scores from first pain assessment post-treatment (Day 1) to Day 30, Day 180, and Day 360
- Changes in NRS pain intensity scores ("average pain over 24 hours") from pre-treatment to Day 360
- Oswestry Disability Index scores (ODI) from Day 30 to Day 360
- Change in Oswestry Disability Index (ODI) scores from pre-treatment to Day 360
- Patient's Global Impression of Change (PGIC) scores from Day 30 to Day 360
- Patient satisfaction with pain management from Day 30 to Day 360
- Percentage of subjects who are in "no disability" determined by ODI scores at Day 360
- Concomitant medication use

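### The ODI standing item in Protocol Appendix 3 prints 3 minutes ahead of 10 minutes, so its ordered options are out of sequence; if scored by position, this puts about 2 ODI points of measurement error on an affected form

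*Protocol*

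**What the plan says.** Protocol Appendix 3 reproduces the questionnaire that subjects complete at Screening and at twelve follow-up times from Day 30 to Day 360. The instruction is "Please answer by checking ONE box in each section for the statement which best applies to you". Each section offers six statements running from least to most limited.

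In Section 6 (Standing), two options without a time limit are followed by these four, in this order:

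- third: "Pain prevents me from standing for more than 1 hour"
- fourth: "Pain prevents me from standing for more than 3 minutes"
- fifth: "Pain prevents me from standing for more than 10 minutes"
- sixth: "Pain prevents me from standing at all"

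In Section 5 (Sitting), the fourth option is "Pain prevents me from sitting more than 30 minutes" and the fifth is "Pain prevents me from sitting more than 10 minutes".

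The SAP lists ODI as a baseline characteristic (section 9.4.2) and names three ODI secondary endpoints in section 9.7.1.2: the scores, the change from pre-treatment, and the percentage of subjects without disability, "determined by ODI scores at Day 360". Sections 9.7.2.2.3 and 9.7.2.2.4 send the first two through the regression analysis used for the primary endpoint. Neither document prints an ODI scoring key or any instruction that corrects the standing item.

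**The concern.** An ordered item works only if each later option describes a worse state. Here the fourth option is a tighter limit than the fifth. A subject who ticks the statement that is literally true can therefore receive a score in the wrong order relative to other subjects, or relative to that subject's own earlier visit. There is also a gap between 1 hour and 10 minutes that the sitting item does not have.

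What is at stake is the accuracy of one of ten items in a secondary outcome. It still deserves attention in this study. The protocol says that the pilot should test whether its outcome measures are workable and should supply a basis for the sample size of a full trial. A faulty item left in place adds avoidable noise to those planning data and may be carried into the next trial.

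**Working it through.** The plan states no figure to reproduce. The check has three steps.

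**1. Is the order broken?** The limits of options three to six, read from Appendix 3, are:

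| Item | 3rd | 4th | 5th | 6th | Falls steadily? |
|---|---|---|---|---|---|
| Standing (minutes) | 60 | 3 | 10 | 0 | No |
| Sitting (minutes) | 60 | 30 | 10 | 0 | Yes |
| Sleeping (hours) | 6 | 4 | 2 | 0 | Yes |

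Of these three timed items, only standing breaks the pattern.

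**2. What happens to the item score?** Assume scoring by position, 0 for the first option to 5 for the sixth. As printed, 60 minutes scores 2, 3 minutes scores 3, 10 minutes scores 4 and inability to stand scores 5. Two corrections would restore the order: a 30-minute fourth option (60, 30, 10, 0) or an exchange of options four and five (60, 10, 3, 0). The documents do not say which was intended, so both are shown. With a 30-minute option, a subject limited to 3 minutes is taken to tick the 10-minute statement.

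| Subject's limit | Score as printed | With a 30-minute 4th option | With 4th and 5th exchanged |
|---|---|---|---|
| 3 minutes | 3 | 4 | 4 |
| 10 minutes | 4 | 4 | 3 |
| About 30 minutes | 2 or 4 (no match) | 3 | 2 or 3 (no match) |

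- The 3-minute subject is one point too low under either correction.
- A subject who improves from 3 to 10 minutes is recorded as 4 − 3 = +1, a worsening. The corrected change would be 4 − 4 = 0 with a 30-minute option, or 3 − 4 = −1 with the exchange.
- Against a 30-minute option, the subject limited to about 30 minutes is off by 2 − 3 = −1 or 4 − 3 = +1, so the error can go either way.

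**3. What is one item point worth?** With all ten sections answered the maximum is 10 × 5 = 50, so one point is 1/50 × 100 = 2.0 ODI percentage points. If the optional sex-life section is skipped the maximum is 9 × 5 = 45, and one point is 1/45 × 100 = 2.2.

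**Reach.** One screening form and twelve follow-up forms make 13 per subject, or up to 13 × 30 = 390 forms. The documents give no basis for the share of subjects who would choose among the affected options. As an illustration only, if 3 of 15 subjects in one arm were each off by 2.0 points in the same direction, that arm's mean would move by 3 × 2.0 / 15 = 0.4 points.

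**The case against.** The strongest objection is that the 3 may be a 30 that lost a digit when the PDF was converted to text. Digits are visibly garbled elsewhere in the available text of the protocol: the clinical assessments schedule in the synopsis shows Day 50 where Appendix 1 has Day 30. This cannot be excluded. However, that schedule is a broken table, whereas the standing item reads cleanly and 30 minutes comes through correctly in the sitting and travelling items. A conversion error is possible but not shown, and the first step of the fix would settle it.

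The second objection is size. The error is about 2 points per affected form, ODI is a secondary outcome, and the same form serves both arms. A subject who ticks the same option at two visits carries no error in the change score. All of this stands, and it limits the point to a minor one.

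A reader might also infer more than the documents support:

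- **That the error always lowers ODI.** It does so for the 3-minute subject. A subject limited to about 30 minutes who ticks the 10-minute option scores too high.
- **That it moves subjects into or out of the no-disability category.** Neither document prints a cut, so this cannot be shown. A subject who cannot stand beyond 3 minutes still scores 3 on this item and is an unlikely borderline case.
- **That 30 minutes is established as the correct wording.** The sitting item suggests it, but exchanging options four and five would also restore the order.

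**Conclusion.** The point holds as a minor defect in the instrument. As printed in Appendix 3, the standing item is out of sequence, and nothing in the protocol or SAP corrects it. The consequence for scores depends on two conditions: that options are scored by position, which the least-to-worst layout supports but no printed key confirms, and that the form subjects actually complete matches the appendix.

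On those conditions an affected form is typically wrong by one item point, in either direction depending on the subject. The damage is chiefly measurement error common to both arms. The documents give no reason to expect it to favour one treatment.

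**What to change.** 1. Compare the standing item on the paper CRF or EDC form with the source instrument. If the form in use is ordered, correct Appendix 3 and nothing more is needed.
2. If the form reads as in Appendix 3, correct the fourth standing option so that the order is restored. The sitting item suggests 30 minutes; take the wording from the source instrument.
3. Flag every ODI completed on the old form. For those forms, report a sensitivity ODI score that omits the standing item, expressed as a percentage of the maximum of the remaining sections. For change scores, omit the item from both forms being compared.
4. State the ODI scoring rule in the SAP, so that scoring by position no longer has to be assumed.

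The cost is one form check. If the error is confirmed, add a form correction, a version flag in the data and one sensitivity summary. No visit, sample size or primary analysis changes.
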